**Table 2-5 CMV prophylaxis**

ATC code	Drug code	WHO preferred term
J05AB	00587301	aciclovir
J05AB	00587302	aciclovir sodium
J05AB	00784201	ganciclovir
J05AB	00784202	ganciclovir sodium
J05AB	01226201	famciclovir
J05AB	01269701	valaciclovir
J05AB	01269702	valaciclovir hydrochloride
J05AB	01319501	penciclovir
J05AB	01542201	valganciclovir
J05AB	01542202	valganciclovir hydrochloride
J05AD	00731301	foscarnet
J06BB	00849701	immunoglobulin cytomegalovirus

### 2.8.4.2 BKV

The incidence of BKV infection will be tabulated for each treatment group:

- Any BKV infection
- BKV infection with a urinary or serological sign
- Clinical or laboratory indicated BKV infection
- BKV infection with an organ involvement (histological evidence)

### 2.8.4.3 New Onset Diabetes

A patient is identified as not having diabetes at baseline if all of the following conditions are met:

- Diabetes was not reported as a medical history in Relevant medical history panel (MedDRA preferred term containing diabetic or diabetes);
- No prior diabetic medication with ATC level 2 code “A10” taken prior to baseline.
- Glucose (random) < 11 mmol/L (200 mg/dl), or fasting glucose measurements < 7 mmol/L (126 mg/dl) at the time of transplantation;

For patients who do not have diabetes at baseline, new onset of diabetes will be identified if any of the following conditions are met:

- Diabetes is reported as an adverse event (MedDRA preferred term containing diabetic or diabetes) with a date of onset (AE start date) post-baseline.
- Any concomitant medication with ATC level 2 code “A10” used in diabetes, if administered for more than 2 consecutive weeks post-baseline.
- Fasting glucose measurements  $\geq 7$  mmol/L (126 mg/dl) post-baseline on two separate occasions, or glucose (random)  $\geq 11$  mmol/l (200 mg/dl) on two separate occasions.

The date of onset will be the earliest date when any of the above conditions is met. Depending on the onset date, a patient will be identified as having DM prior to baseline if the date is prior to or at baseline, and a patient will be identified as have DM post-baseline if the date is after baseline.

In addition, new onset diabetes will be identified with a second definition below:

New onset diabetes, defined in patients who were not diabetic at baseline, will be identified from the NODM NMQ in patients where diabetes is recorded as reason for a medication given post-baseline lasting for 30 days or more (Medications will be identified by searching ATC level 2 code of A10).

Notes: The NODM NMQ includes all PTs with root ”diab” included in the NODM SMQ plus the PT “Hyperglycaemic hyperosmolar nonketotic syndrome” which includes the LLT “Diabetic hyperosmolar non-ketoacidosis”. In more descriptive terms, this would mean that the NODM NMQ will include two sets of Preferred Terms (PTs) as follows:

All PTs with root ”diab” included in the NODM SMQ

PTs of “Hyperglycaemic hyperosmolar nonketotic syndrome” with LLT as “Diabetic hyperosmolar non-ketoacidosis”.

The expansions for the acronyms are as follows: NODM= New-Onset Diabetes Mellitus, NMQ = Novartis MedDRA Queries, SMQ =Standard MedDRA query, LLT =Lowest Level Term, PT = Preferred Term.

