5.5.6 Rescue medication

Not applicable.

5.5.7 **Concomitant Treatment**

The investigator should instruct the subject to notify the study site about any new medications he/she takes after the subject was enrolled into the study. All medications, procedures and significant non-drug therapies (including physical therapy and blood transfusions) administered after the subject was enrolled into the study will be recorded on the Concomitant Medications CRF or the Surgical and Medical Procedures CRF respectively.

CMV prophylaxis

Cytomegalovirus (CMV) pre-emptive therapy and/or prophylaxis is recommended for all donor CMV positive/recipient CMV negative cases and considered for all recipients who are CMV positive. It is recommended that CMV prophylaxis be administered for a minimum of three months after transplantation. Prophylactic treatment with i.v. ganciclovir or oral valgan ciclovir is recommended and will be administered according to local practice, taking into account dose adjustments based on renal function. CMV prophylaxis is also recommended following antibody treatment of acute rejection episodes (see Section 5.5.5 above). Such prophylaxis should be recorded on the Concomitant Medications CRF.

Pneumocystis jirovecii (Pneumocystis carinii) pneumonia prophylaxis

All subjects will be started on trimethoprim-sulfamethoxazole, starting when oral medication can be tolerated and continuing until at least six months post-transplant. After six months, subjects will be treated per local practice. Aerosolized pentamidine or dapsone may be administered to subjects who are unable to tolerate trimethoprim-sulfamethoxazole.

These prophylactic treatments above must be applied consistently across the study population at each given center to avoid bias and confounding in the results. Such prophylaxis should be recorded on the Concomitant Medications CRF.

Treatment of hyperlipidemia

During the course of the study, the lipid profile will be monitored. Lipid lowering medications should be administered according to guidelines and local practice.

The combination of HMG-CoA reductase inhibitors concomitantly with fibrates should be avoided, due to the increased risk of myopathy and rhabdomyolysis in combination with cyclosporine. If combination therapy is needed, ezetimibe should be used in combination with statins. Lipid lowering therapy should be optimized before dosage reduction of study medication is considered.

Hepatitis B (HBV) prophylaxis

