- 2. The Baseline visit covers the transplant period from 24 hr prior to surgery until randomization or randomization failure. Randomization must occur within 24 hr of completion of transplant surgery and post-transplant criteria for randomization (e.g. ability to take oral medication) must be met. Day 1 is the day of first dose of study drug post-randomization and for subsequent visits one week is 7 days and one month is 30 days, thus the Week 1 visit is on the seventh day from Day 1.
- 3. Viral serology includes HCV, HIV, HBV surface antigen, CMV and EBV. Measurements made within the last 6 months will be accepted, otherwise these tests should be performed within one week of randomization.
- 4. Only for females of child bearing potential, serum pregnancy tests should be carried out according to local practice. Local result must be available and negative prior to randomization.
- 5. First dose of everolimus or MPA together with applicable CNI (tacrolimus or cyclosporine) must be given immediately following randomization and within 24 hr of transplantation. Pre-transplant immunosuppression, including induction therapy and any CNI or MPA should be recorded on the Concomitant medication CRF under the immunosuppressive category.
- 6. Blood draws for everolimus, tacrolimus and cyclosporine (as applicable) trough concentrations should be performed locally as shown and additionally 5 days ± 2 days following each clinic visit in which tacrolimus, cyclosporine or everolimus doses are changed. Subject clinical management should be based on these local trough levels. At certain centers, by agreement with the sponsor, central analysis of everolimus may be performed.

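### The new-onset diabetes rule excludes a patient for any A10 record before randomisation, although after baseline A10 counts only with more than 2 consecutive weeks of use in diabetes

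*SAP*

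**What the plan says.** SAP 2.8.4.3 first sets a screen: "A patient is identified as not having diabetes at baseline if all of the following conditions are met". There are three conditions: no diabetes in the medical history, "No prior diabetic medication with ATC level 2 code" A10 before baseline, and glucose below a stated threshold at transplantation. Failing any one makes the patient diabetic at baseline.

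The case rule follows: "For patients who do not have diabetes at baseline, new onset of diabetes will be identified if any of the following conditions are met". The alternatives are a diabetes adverse event, an A10 drug used in diabetes "if administered for more than 2 consecutive weeks post-baseline", or raised glucose on two occasions. A second definition carries the same restriction, "New onset diabetes, defined in patients who were not diabetic at baseline", and needs diabetes to be "recorded as reason for a medication given post-baseline lasting for 30 days or more".

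On timing, SAP 2.1.1.4 takes the baseline value as the last before randomisation, and SAP Table 4-1 ends the baseline window at randomisation. Protocol Table 6-1, footnote 2, says: "The Baseline visit covers the transplant period from 24 hr prior to surgery until randomization or randomization failure". The same footnote allows randomisation up to 24 hours after surgery ends. On capture, Protocol 5.5.7 requires that medications "administered after the subject was enrolled into the study will be recorded on the Concomitant Medications CRF", and the Protocol glossary puts enrolment at informed consent. SAP 2.4.3 sets no minimum duration for a prior medication.

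**The concern.** The A10 condition in the screen is much looser than the A10 criterion in the case rule, and the SAP gives no reason for the difference. The period in which a single record is enough includes the operation, the hours after it and any pre-transplant steroids (Protocol 5.5.4). Insulin given once in that period, for a transient glucose rise or for another reason, carries an A10 code.

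The classification cannot be reversed later. Both definitions apply only to patients who passed the screen, so a later diabetes adverse event, repeated high glucose or months of treatment does not bring the patient back.

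New-onset diabetes is named among the other secondary objectives (Protocol 2.2) and is to be reported with risk ratios and confidence intervals (SAP 2.8.2). The baseline diabetes rate is also tabulated (SAP 2.3.2). What is at stake is the absolute incidence, the baseline rate and some precision.

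**Working it through.** The documents state no new-onset diabetes rate or power for this endpoint, so there is no figure to reproduce. The check is of the rule's logic, followed by an illustration of size.

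**1. The rule applied to one patient.** Take a patient with no diabetes history and acceptable glucose, and vary the consecutive days of A10 use. The last column applies the more-than-14-day test before baseline as well.

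| Days of A10 | Before baseline: at risk under the SAP rule? | Same days after baseline: A10 criterion met? | Before baseline: at risk under a more-than-14-day test? |
|---|---|---|---|
| 0 | yes | no | yes |
| 1 | no | no | yes |
| 3 | no | no | yes |
| 14 | no | no | yes |
| 15 | no | yes (if used in diabetes) | no |

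From 1 to 14 days, the same exposure is enough to class the patient as diabetic before baseline but does not meet the A10 criterion after it.

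**2. Does the peri-operative period fall before baseline?** SAP 2.1.1.4 and Table 4-1 both tie baseline to randomisation, and Protocol Table 6-1 places randomisation after surgery. On that reading, insulin given during surgery or in the hours before randomisation counts as prior. SAP 2.1 names the date of transplant as the baseline reference, but in a rule for choosing among several values in a window. If that anchor were used here, doses first given after the transplant would not count and fewer patients would be affected; pre-operative doses still would.

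**3. Size, on assumptions.** From the documents: 2040 patients planned (Protocol 3.1). Assumed, and not in the documents: 70% truly non-diabetic; a share q of these with any A10 record before randomisation; a new-onset rate of 15% in the rest; a relative risk r of 1 or 2 in those with the record.

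- Truly non-diabetic: 0.70 × 2040 = 1428.
- Removed, at most: 1428q.
- Share of true cases missed: rq / [(1 − q) + rq]. The 15% cancels.

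| q | Removed (upper bound) | Missed share, r = 1 | Missed share, r = 2 |
|---|---|---|---|
| 5% | 71 | 5% | 0.10/1.05 = 9.5% |
| 10% | 143 | 10% | 0.20/1.10 = 18% |
| 20% | 286 | 20% | 0.40/1.20 = 33% |

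These are upper bounds. If a share s of the patients with a brief A10 record also fail the glucose condition, the number removed by the A10 condition alone is 1428q(1 − s), and s is unknown.

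**4. Effect on the rate.** Take as denominator the patients classed as non-diabetic, which 2.8.4.3 implies but does not state. With r = 1 the observed rate stays at 15% and only cases and precision are lost. With r = 2 the rate in all non-diabetics would be 0.15 × (1 + q) = 15.75%, 16.5% or 18% for the three values of q, against 15% observed.

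**5. Sensitivity to baseline diabetes.** If 15% to 25% of 1020 patients per arm are truly diabetic, 765 to 867 are not. With q from 5% to 20%, at most 38 (765 × 0.05) to 173 (867 × 0.20) per arm are removed.

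**The case against.** The strongest defence is that the two rules do different jobs. The baseline rule decides who can count as new onset; the post-baseline rule identifies cases. A strict screen is a defensible conservative choice, because glucose disturbance treated before the first randomised dose began before the regimen under test. That has some force, and it is why the present rule should stay in the report and not simply be replaced.

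Several stronger readings are tempting and not supported:

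- A reader might infer that the SAP itself treats A10 use of 2 weeks or less as proof of no diabetes. It does not. Short use after baseline fails one of three alternatives; a diabetes adverse event or two raised glucose values would still qualify.
- A reader might infer that every patient given peri-operative insulin would be recovered by changing the A10 condition. Those who also fail the glucose condition would stay excluded, and a patient given insulin for high glucose may well be one of them.
- A reader might infer that the affected cases vanish from the report. The general adverse event tables (SAP 2.8.1) have no baseline-diabetes restriction. SAP 2.8.3 also lists new-onset diabetes under a program-level definition that is not visible here, so it cannot be assumed to share this screen.

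It could also be said that the words for diabetic medication imply an indication. The only test the baseline condition gives is the ATC code; use in diabetes is specified only after baseline.

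**Conclusion.** The point holds for the two definitions in SAP 2.8.4.3. Any A10 record before baseline, whatever its duration or reason, removes a patient who passes the history and glucose conditions, and neither definition can then count that patient as a case. Baseline diabetes is overstated and the at-risk set is too small. Incidence is understated if the removed patients have a higher risk than the rest, which is plausible but not shown.

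A reader might infer a biased comparison between arms. The documents do not support that: the exclusion rests on pre-randomisation data and should be balanced in expectation.

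The size is unknown. The figures of 71 to 286 patients and 5% to 33% of true cases depend wholly on the assumed inputs, are upper bounds because of overlap with the glucose condition, and take randomisation as the anchor. This is an inconsistency in a secondary safety endpoint that is cheap to correct; it does not touch the primary or key secondary analyses.

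**What to change.** In the baseline rule of SAP 2.8.4.3, count A10 use only if its recorded reason is diabetes or it was taken for more than 2 consecutive weeks before randomisation. Keep the history and glucose conditions. State that baseline means randomisation for this derivation.

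Two details must be settled with it:

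- **Courses that straddle baseline.** The SAP assigns diabetes to before baseline when the onset date is at or before it, and gives no onset date for an A10 course already running. Count only post-baseline days towards the 2-week criterion and set the onset date after baseline.
- **Partial start dates.** Rule (A) in SAP 4.2.4.1 turns a partial start date in the month of treatment start into a date after treatment start. Applied to peri-operative A10, it would move the start past baseline. Exempt these records from that rule in this derivation.

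Report the new-onset diabetes incidence and risk ratio under both the rule as it stands and the revised rule.

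The cost is a few lines of SAP text, one changed derivation and one repeated table. Medication dates already have handling rules in the SAP, and the second definition already relies on a recorded reason; wholly missing dates are not imputed, which is a small limitation. The downside is that a few undiagnosed diabetics who recently started A10 for another recorded reason may enter the at-risk set. The paired report would show the effect.

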- 7. Central laboratory tests at each visit indicated include: **Biochemistry** (sodium, potassium, chloride, calcium, Cystatin C, magnesium, inorganic phosphate, urea, creatinine, uric acid, AST, ALT, alkaline phosphatase, total bilirubin, CPK, lipase and amylase); Hematology (platelets, hemoglobin, red blood cell (RBC), white blood cell (WBC) and differential count): Lipids: total cholesterol, HDL, LDL and triglycerides Urinalysis (protein, creatinine, albumin, glucose; proteinuria and albuminuria per 24hr period will be estimated from spot protein/creatinine and albumin/creatinine ratios). For subjects who have discontinued study regimen who continue in the study to Month 24 all central laboratory assessments, including serum creatinine for renal function, should be performed, where no central laboratory serum creatinine is available local laboratory serum creatinine should be obtained. HbA1c and fasting plasma glucose will also be carried out by the central laboratory at Week 4 and Months 4, 6, 9, 12 18 and 24. At certain centers, in agreement with the sponsor, central analysis of everolimus levels may be performed.
- 8. Induction therapy (basiliximab or rATG) should be recorded on the Concomitant Medications CRF under the Immunosuppressive Medications category. Pre-transplant CNI or MPA, if used, should be also recorded on the Concomitant medication CRF under the immunosuppressive category.
- All serious adverse events, serious infections and pregnancies must be reported from informed consent until 30 days after the last study visit post randomization (i.e. to the Month 12/24 visit or early discontinuation from study).
- 10. All subjects are expected to continue in the study to Month 24 regardless of whether they are on or off randomized study regimen, if subjects discontinue randomized study regimen they should continue on standard of care and attend study visits to M24. Any permanent discontinuation of the randomized study regimen should be recorded on the appropriate DAR(s) (everolimus MPA, tacrolimus or cyclosporine as needed). Post discontinuation of study regimen the immunosuppressive

Amended Protocol Version v01 Clean

Study Period	Screen	ning¹	Treatm	ent to	Month	12						Extens Treatn to Mor	nent
Visit	SCR	BL ²	D4	W1	W2	W4	M2	M4	М6	М9	M12	M18	M2 4
Visit Number	1	99	101	102	103	104	105	106	107	108	199	201	299

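### The baseline no-diabetes rule in SAP 2.8.4.3 needs a blood glucose that the protocol does not schedule, has no rule for a missing value, and passes discordant values as non-diabetic

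*SAP*

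**What the plan says.** SAP 2.8.4.3 sets the at-risk group first: "A patient is identified as not having diabetes at baseline if all of the following conditions are met". There are three conditions: no diabetes in the medical history, no antidiabetic drug (ATC A10) before baseline, and "Glucose (random) < 11 mmol/L (200 mg/dl), or fasting glucose measurements < 7 mmol/L (126 mg/dl) at the time of transplantation".

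Among those patients, new onset is met by a diabetes adverse event, by more than two weeks of an A10 drug, or by glucose. The glucose criterion is fasting values of at least 7 mmol/L "post-baseline on two separate occasions, or glucose (random") of at least 11 mmol/L, again twice. A second definition in the same section has the same entry gate: "New onset diabetes, defined in patients who were not diabetic at baseline, will be identified from the NODM NMQ".

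On data collection, protocol Table 6-1 marks the central laboratory at the Baseline visit. Footnote 7 gives the biochemistry content as "sodium, potassium, chloride, calcium, Cystatin C, magnesium, inorganic phosphate, urea, creatinine, uric acid, AST, ALT, alkaline phosphatase, total bilirubin, CPK, lipase and amylase". The only glucose in the per-visit panel is in urinalysis: "protein, creatinine, albumin, glucose; proteinuria and albuminuria per 24hr period will be estimated". Blood glucose appears separately: "HbA1c and fasting plasma glucose will also be carried out by the central laboratory at Week 4", and then at Months 4, 6, 9, 12, 18 and 24.

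SAP 2.1.1.4 takes as baseline the last non-missing value before randomization. SAP 2.8.4.3 does not say what to do when no glucose is available at transplantation.

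**The concern.** The rule depends on a measurement that the visit schedule does not provide. All conditions must hold, so a missing glucose is enough to stop a patient being classed as non-diabetic, even with a clean history and no A10 drug. Two programmers could reasonably differ here. One would drop such patients and the other would treat missing as acceptable, and the SAP does not choose between them. The denominators could differ considerably.

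The *or* is a separate fault. Diabetic range is defined by either glucose type being high, so its absence requires both to be below their cut-offs when both are known. The bullet asks for only one.

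New-onset diabetes is a named secondary objective (protocol 2.2), and SAP 2.8.2 reports it with risk ratios and 95% confidence intervals. Baseline diabetes is also summarized (SAP 2.3.2). If that summary takes diabetic as everyone not classed non-diabetic, patients without a glucose would be counted as diabetic at baseline.

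**Working it through.** There is no plan figure to reproduce and no sample-size arithmetic. The check is a truth table, followed by a comparison of the rule with the schedule.

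**Step 1. Truth table for the glucose bullet.** Each glucose type is below its cut-off, in the diabetic range, or not measured. The third column applies the bullet as written. The fourth requires every available value to be below its cut-off.

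| Random (mmol/L) | Fasting (mmol/L) | Bullet as written | All available values below cut-off |
|---|---|---|---|
| < 11 | < 7 | met | met |
| < 11 | ≥ 7 | **met** | **not met** |
| < 11 | none | met | met |
| ≥ 11 | < 7 | **met** | **not met** |
| ≥ 11 | ≥ 7 | not met | not met |
| ≥ 11 | none | not met | not met |
| none | < 7 | met | met |
| none | ≥ 7 | not met | not met |
| none | none | **not met** | **undetermined** |

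The columns differ in three of the nine cells: the two discordant pairs and the empty pair. With only one value, the bullet works. A lone fasting value of 7 or more fails it, as it should.

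**Step 2. What happens in the discordant cells.** Take fasting 9 and random 10, with no history and no A10 drug. The bullet is met through the random value, so the patient is at risk. Two post-baseline fasting values of 7 or more then make a new-onset case. The fault also runs the other way, with random at least 11 and fasting below 7.

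**Step 3. Whether the onset-date sentence repairs this.** The section adds that "a patient will be identified as having DM prior to baseline if the date is prior to or at baseline". But onset is the earliest date on which a new-onset criterion is met, and the fasting criterion counts only post-baseline values on two occasions. A high fasting value at transplantation therefore cannot give an earlier onset date.

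**Step 4. Which cell the schedule leads to.** The Baseline biochemistry list has no blood glucose. Urine glucose cannot be compared with cut-offs of 7 and 11 mmol/L. Fasting plasma glucose starts at Week 4, after randomization, so SAP 2.1.1.4 excludes it as a baseline value. Footnote 7 schedules no random blood glucose at any visit. A patient followed exactly to schedule therefore falls in the last row, where the literal result is *not met* and the SAP gives no alternative.

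**Step 5. Whether the second definition escapes.** It does not, because it is limited to patients without diabetes at baseline. It does require a diabetes medication lasting at least 30 days, so glucose values alone cannot create a case under it.

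**The case against.** The best defence of the *or* is that it means the cut-off for whichever type was measured. On that reading, single values are handled correctly and only patients with two disagreeing values remain unclear. Since no baseline blood glucose is scheduled, such patients may be few. This stands, and it is why the *or* is the secondary part of the point. The SAP should still say so if that is the intention.

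A reader might infer that no baseline glucose will exist and that nearly everyone drops out of the analysis. The documents do not support that. SAP 4.1 brings unscheduled assessments into the visit windows, protocol Appendix 1 and SAP 4.6.1 give notable limits for glucose, and SAP 2.8.4.3 itself uses random glucose that footnote 7 does not schedule. The authors seem to expect values from elsewhere, and the laboratory manual mentioned in protocol 6.5.4 is not available here. What holds is narrower: the source is not named and the missing-value rule is absent.

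A reader might also infer that existing diabetics inflate the new-onset rate by several percentage points, or that the comparison is biased toward one arm. Neither follows. Any such percentage needs the share of patients with discordant values and a clean history, which the documents do not give. Classification rests on pre-randomization data, so errors should be similar in the two arms in expectation.

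Finally, SAP 2.8.3 lists new-onset diabetes among events defined in a program-level case retrieval sheet, apparently by another route. That does not resolve the two definitions in 2.8.4.3.

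**Conclusion.** The point holds as a fault in a derivation rule. Followed literally, SAP 2.8.4.3 removes from the at-risk set any patient with no recorded glucose at transplantation, and the protocol does not schedule one. Where both glucose types exist and disagree, it also admits a patient with one value in the SAP's own diabetic range.

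No magnitude is claimed. The number of patients without a value, and the number with discordant values, cannot be derived from the documents. The missing-value gap probably matters more in practice, because discordance requires two values and the schedule provides neither.

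The effect is confined to the new-onset diabetes incidence and the baseline diabetes summary. The primary and key secondary tests do not use this classification. The conclusion assumes that the bullet is programmed as written and that footnote 7 is the full scheduled blood glucose collection. If the laboratory manual adds a baseline glucose, the missing-value part shrinks and the *or* remains.

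**What to change.** Keep the SAP's time point and replace the third bullet with wording such as:

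> No glucose value available at the time of transplantation is in the diabetic range (random ≥ 11 mmol/L or fasting ≥ 7 mmol/L). A patient with no value is classified by diabetes history and prior A10 medication alone.

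Also name the data source for this glucose (central, local or unscheduled) and report by arm how many patients lack one. The time point should not be widened to any earlier reading. Post-baseline onset by glucose needs two occasions, and a wider window would let one old or isolated value exclude a patient.

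The same edit can correct the cross-references in SAP 2.3.2 and 2.8.2, which point to 2.8.3.3 although the rule is in 2.8.4.3.

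The cost is a short SAP change, an adjustment to the derivation program and one extra count by arm, with no new data collection. The downside is that some undiagnosed diabetics without a baseline glucose stay in the at-risk set and may later count as new cases. The count of missing values shows how far that could matter.
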